### **1.22.5 *Protocol Deviations***

#### **1.22.5.1 *Anticipated Deviations***

Anticipated deviations are events that the Investigator anticipates or would like to be aware of prior to when they occur. See Table 7. An anticipated deviation must be reported using the EDC and discussed with the Sponsor prior to its occurrence. The Sponsor will assess the requested deviation for a possible effect on safety or rights of the patient or on the impact to study data or quality. The Medical Monitor will be consulted for opinion regarding anticipated deviations.

Table 7. Protocol Deviations (Anticipated)	
Anticipated Deviations	Action Required
Patient does not return for scheduled visit post-infusion follow-up	Attempt to call at least two times. Document call times on phone log. Contact by registered letter if still unresponsive.
Visit dates outside of range specified in protocol	Note correct time/day on CRF and keep a log of same for entire study

#### **1.22.5.2 *Unanticipated Deviations***

Unanticipated deviations are events not foreseen by the Investigator, and typically reflect reactions or judgment calls by the Investigator. Unanticipated deviations can also result from Investigator or staff error. An unanticipated deviation must be reported to the Sponsor using the EDC as soon as it is recognized. Report can primarily be verbal; however, it must be followed with written documentation. The written report must explain the reason and rationale for the deviation, if the deviation affects the safety or rights of the patient or additional patients and recommended corrective actions. The Sponsor will formulate an appropriate follow-up plan (e.g., additional site training). The Medical Monitor may be consulted for opinion regarding unanticipated deviations. Any deviation to the protocol will be documented in study records. Deviations that may have an effect on the safety or rights of the patient or the integrity of the study must be promptly reported to the IRB of record. Documentation of any actions taken by the IRB of record related to the deviation report will be provided to the study Sponsor.

### **1.22.6 *Adverse Events and Unanticipated Problems***

#### **1.22.6.1 *Definition of Terms***

##### **A. Adverse Event (or Adverse Experience):**

Any untoward medical occurrence in a patient administered a pharmaceutical product and which does not necessarily have to have a causal relationship with this treatment. An

adverse event (AE) can therefore be any unfavorable and unintended sign (including an abnormal laboratory finding, for example), symptom or disease temporally associated with the use of a medicinal product, whether or not considered related to the medicinal product.

An abnormal laboratory finding that requires medical or surgical intervention or leads to study treatment interruption or discontinuation must be recorded as an AE (or SAE, if applicable). If the changes from baseline are mild and in the opinion of the investigator not clinically significant, the event is not considered an AE, however, the investigator should continue to carefully monitor the values. Laboratory tests may be repeated, as clinically indicated, without prior approval by Sponsor or Medical Monitor. Special attention must be paid to the results of coagulation parameter results not within reference ranges.

**B. Adverse Drug Reaction (ADR):**

In the clinical experience with a new medicinal product or its new usages, particularly as the therapeutic dose(s) may not be established all noxious and unintended responses to a medicinal product related to any dose should be considered adverse drug reactions. The phrase "responses to a medicinal product" means that a causal relationship between a medicinal product and an adverse event is at least a reasonable possibility, *i.e.*, the relationship cannot be ruled out.

**C. Unexpected ADR:**

An adverse reaction, the nature or severity of which is not consistent with the applicable product information (e.g., Investigator's Brochure for an unapproved investigational medicinal product).

**D. SAE or ADR:**

An adverse event that occurs during a clinical investigation and if suspected to be medicinal product-related (adverse drug reactions), and might be significant enough to lead to important changes in the way the medicinal product is developed (e.g., change in dose, population, needed monitoring, consent forms. These events result in:

- Death.
- Life-threatening situation (patient is at immediate risk of death).
- In-patient hospitalization (excluding those for study therapy or placement of an indwelling catheter, unless associated with other SAEs).
- Prolongation of existing hospitalization.
- Persistent or significant incapacity or substantial disruption of the ability to conduct normal life functions.
- Congenital anomaly/birth defect in the offspring of a patient who received study drug.
- Other: important medical events that may not be immediately life- threatening or result in death or hospitalization, but based upon appropriate medical and scientific judgment, may jeopardize the patient or may require medical or surgical intervention to prevent one of the outcomes listed above.

Examples of such events are as follows:

- Intensive treatment in an emergency room or at home for allergic bronchospasm.
- Blood dyscrasias or convulsions that do not result in hospitalization.
- Development of drug dependency or drug abuse.

**E. Clarification of SAE**

- Death is an outcome of an AE, and not an AE in itself. In reports of death due to "Disease Progression," where no other information is provided, the death will be assumed to have resulted from progression of the disease being treated with the study treatment(s).
- All deaths, regardless of cause or relationship, must be reported for patients on study and for deaths occurring within 30 (+2) days of last study treatment or within 30 (+2) days of last study evaluation, whichever is longer.
- "Occurring at any dose" does not imply that the patient is receiving study treatment at the time of the event. Dosing may have been given as treatment cycles or interrupted temporarily before the onset of the SAE, but may have contributed to the event.
- "Life-threatening" means that the patient was at immediate risk of death from the event as it occurred. This does not include an event that might have led to death if it had occurred with greater severity.
- Complications that occur during hospitalizations are AEs. If a complication prolongs the hospitalization, it is a SAE.
- "In-patient hospitalization" means the patient has been formally admitted to a hospital for medical reasons, for any length of time. This may or may not be overnight. It does not include presentation and care within an emergency department.
- The Investigator should attempt to establish a diagnosis of the event on the basis of signs, symptoms, and/or other clinical information. In such cases, the diagnosis should be documented as the AE and/or SAE and not the individual signs/symptoms.

A distinction should be drawn between seriousness and severity of AEs. An AE that is assessed as severe should not be confused with a SAE. Severity is a category utilized for rating the intensity of an event, and both AEs and SAEs can be assessed as severe. An event is defined as "serious" when it meets one of the predefined outcomes described above.

**1.22.6.2 Relationship to Investigational Product**

The site PI must assign a relationship of each AE to the receipt of the investigational product. The PI will use clinical judgment in conjunction with the assessment of a plausible biologic mechanism, a temporal relationship between the onset of the event in relation to receipt of the investigational product, and identification of possible alternate etiologies including underlying disease, concurrent illness, or concomitant medications. The following guidelines should be used to assess the relationship of an AE to study product administration and **ONLY THE INVESTIGATOR (QUALIFIED MD/DO) CAN MAKE THIS DETERMINATION:**

- Not related: No relationship to investigational product. Applies to those events for which evidence exists that there is an alternate etiology.

- Unlikely: Likely unrelated to the investigational product. Likely to be related to factors other than investigational product, but cannot be ruled out with certainty.
- Possibly: An association between the event and the administration of investigational product cannot be ruled out. There is a reasonable temporal association, but there may also be an alternative etiology such as the patient's clinical status or underlying factors including other therapy.
- Probably: There is a high degree of certainty that a relationship to the investigational product exists. There is a reasonable temporal association, and the event cannot be explained by known characteristics of the patient's clinical state or factors including other therapy.
- Definite: An association exists between the receipt of an investigational product and the event. Any association to other factors has been ruled out.

#### **1.22.6.3 Severity Assessment**

All AEs will be assessed for severity by the PI. Inherent in this assessment is the medical and clinical consideration of all information surrounding the event including any medical intervention required. The CDC National Healthcare Safety Network Hemovigilance Module criteria will be used to help define transfusion-related events. The NCI Common Terminology Criteria (CTCAE version 4.0, June 14, 2010) for toxicity grade will be used to assign the severity for all AEs (transfusion and non-transfusion related) (HHS-2010). The criteria below may be used for any symptom not included in the grading scale. Any Grade 4 (life-threatening) or Grade 5 (fatal) AE must be reported as an SAE.

- Mild Grade 1 Does not interfere with routine activities Minimal level of discomfort
- Moderate Grade 2 Interferes with routine activities Moderate level of discomfort
- Severe Grade 3 Unable to perform routine activities Significant level of discomfort
- Life-threatening Grade 4 Hospitalization or emergency room visit for potentially life-threatening event
- Fatal Grade 5 Results in Death

#### **1.22.6.4 Adverse Event Reporting**

The PI is responsible for reporting all adverse events or unanticipated events to the local IRB, as required, and to Cellphire on a schedule related to the seriousness of the event. A case report form will be provided for these reports. Events that meet the definition of "serious," including unexpected adverse reactions (SUSARs), thrombotic adverse events, and deaths as described above, must be entered into the electronic data capture (EDC).

All SAEs must be reported to Cellphire and or Sponsor's designee, the Contract Research Organization (CRO), in the EDC within 24 hours of the Investigator becoming aware of the SAE. If the site is unable to enter the event information into EDC for any reason the site can alternatively complete the paper SAE Form, which should be faxed/mailed within 24 hours from the point in time when the investigator becomes aware of the SAE. In addition, all SAEs that occur up to and including 30 days after administration of Thrombosomes must be reported to

the Sponsor or Sponsor's designee within 24 hours from when the investigator becomes aware of the SAE.

To report an SAE, sites will enter the SAE information into the EDC or complete an SAE Report and send the SAE report to the CRO, Clinipace Worldwide, Inc.

The investigator must report new significant follow-up information for these events to the Sponsor's designee immediately (i.e., no more than 24 hours after becoming aware of the information).

Cellphire is responsible for reporting to the DMC and the FDA according to the charter, policies and applicable guidance or regulations.

### ***1.22.7 Study Forms and Recording of Information***

It is the Investigator's obligation to ensure that all Case Report Forms and data collection instruments are accurate and complete. All study forms must be signed and dated by the Principal Investigator or designee, to attest that they are an accurate and complete record. A Signature and Delegation log will be completed and signed by the Principal Investigator during the training/initiation visit and kept as a part of the study records.

### ***1.22.8 Continuing Review and Reporting***

The IRB of record requires approval of all protocol amendments, acceptance of continuing review reports, reporting of protocol deviations and unexpected serious adverse drug reactions. A copy of the approved continuing review report and the local IRB approval notification may be submitted by Cellphire to the responsible Biomedical Advanced research and Development Authority (BARDA) representative or the Contracting Officer's Representative (COR) as

appropriate. A copy of the final report and local IRB approval notification may be submitted to BARDA as soon as these documents become available.

Additionally, BARDA requires reporting of any pending compliance inspection/visit by the FDA, OHRP or other government agency concerning the research, the issuance of Inspection Reports, FDA Form 483, warning letters or actions taken by any Regulatory Agencies including legal or medical actions and any instances of serious or continuing noncompliance with the regulations or requirements must be reported immediately to the responsible BARDA representative or the COR as appropriate.

### ***1.22.9 Applicable Regulatory Requirements***

The conduct of this clinical trial will adhere to the following regulations:

- 21 CFR Parts 11, 50, 54, 56, 312
- 21 CFR 600-640 subparts A, D, G
- 45 CFR 46, Protection of Human Subjects
- 32 CFR 219.103, Assurance of Compliance for the Protection of Human Research Subjects
- Health Insurance Portability and Accountability Act of 1996 (HIPAA)
- FDA guideline “Good Clinical Practice: Consolidated Guideline” (ICH E6)

#### **1.22.10.2 Confidentiality of Patient Information**

Cellphire, Inc or its designees, employees of FDA or other regulatory authorities, the IRB of record, may consult source documents in order to verify data, and as such, confidentiality cannot be guaranteed. The study records and laboratory specimens will be stored in a confidential manner and will be coded to protect the patient's confidentiality.

#### ***1.22.11 Security of Investigational Products***

Investigational products will be stored within a secure, limited access enclosure at each investigative site. Access will be provided to only the Investigator and his designee(s) responsible for product storage, preparation, tracking and usage. Investigational product accountability will be maintained.

#### ***1.22.12 Shipping of Specimens***

It is the Investigator's responsibility to ensure that there are trained personnel available to ship diagnostic specimens following DOT/IATA regulations and site's Standard Operating Procedures.

#### ***1.22.13 Clinical Trial Registration***

Information concerning this Phase I clinical trial will be registered on [www.clinicaltrials.gov](http://www.clinicaltrials.gov) prior to study initiation pursuant to US Public Law 110-85, Title VIII, and Section 801.

## Appendix A- Modified WHO Bleeding Score

(Adapted from Supplement from Slichter SJ, Kaufman RM, Assmann SF, et al. Dose of prophylactic transfusions and prevention of hemorrhage. N Engl J Med 2010;362:600-13)

	Grade 1	Grade 2	Grade 3
Oral and nasal	
 
Oropharyngeal bleeding – total duration of all episodes in previous 24 hours <math>\leq</math> 30 minutes*
 
Petechiae of oral mucosa
 
Epistaxis – total duration of all episodes in previous 24 hours <math>\leq</math> 30 minutes*
 
	
 
Oropharyngeal bleeding – total duration of all episodes in previous 24 hours <math>></math> 30 minutes*
 
Epistaxis – total duration of all episodes in previous 24 hours <math>></math> 30 minutes*
 
	
 
Any bleeding requiring RBC transfusion over routine transfusion needs**
 

Skin, soft tissue, musculoskeletal	
 
Petechiae of skin
 
Purpura <math>\leq</math> 1 inch diameter
 
One or more spontaneous hematomas in the soft tissue or muscle <math>></math> 1 inch
 
	
 
Purpura <math>></math> 1 inch diameter
 
Spontaneous hematoma in deeper tissues
 
Joint bleeding (confirmed by aspiration, imaging study or other accepted technique)
 
	
 
Any bleeding requiring RBC transfusion over routine transfusion needs**
 

Gastrointestinal	
 
Positive stool occult blood test
 
	
 
Melanotic stool
 
Hematochezia – visible red blood mixed in stool, not requiring a transfusion
 
Hematemesis – Grossly visible blood in emesis or in nasogastric drainage tube (not related or secondary to swallowed blood)
 
	
 
Any bleeding requiring RBC transfusion over routine transfusion needs**
 

Genitourinary	
 
Any biochemical or microscopic Hb/RBCs without red urine
 
Abnormal vaginal bleeding (Unexpected bleeding out of normal cycle OR Bleeding heavier than normal OR Breakthrough bleeding (patient on hormonal therapy to prevent bleeding)) with spotting
 
	
 
Gross/visible hematuria without need for transfusion
 
Abnormal vaginal bleeding (Unexpected bleeding out of normal cycle OR Bleeding heavier than normal OR Breakthrough bleeding (patient on hormonal therapy to prevent bleeding)) more than spotting
 
	
 
Any bleeding requiring RBC transfusion over routine transfusion needs**
 

Pulmonary		
 
Hemoptysis – Visible blood
 
Blood in broncho-pulmonary lavage, or blood tinged sputum (excluding those with nose or oropharyngeal bleeding)
 
	
 
Any bleeding requiring RBC transfusion over routine transfusion needs**
 

Body Cavity		
 
Visible blood in body cavity fluid (e.g. red cells apparent in fluid aspirate) short of criteria for Grade 3 or 4
 
	
 
Grossly bloody body cavity fluids and organ dysfunction with symptoms, and/or need to intervene
 

[figure not shown]
	Grade 1	Grade 2	Grade 3
Central Nervous System		
 
• Retinal bleeding without visual impairment
 
• Lumbar puncture with blood (<math>>5</math> RBC/<math>\mu</math>L in CSF on microscopic analysis and non-traumatic tap), no symptoms and no visible red color
 
	(e.g. to aspirate), and/or need for transfusion
Invasive Sites	
 
• Bleeding at invasive sites (venipuncture sites, intravenous lines or catheter exit sites): active oozing at site for a cumulative total of <math>\leq 1</math> hour in the previous 24 hours
 
	
 
• Bleeding at invasive sites (venipuncture sites, intravenous lines or catheter exit sites): active oozing at site for a cumulative total of <math>> 1</math> hour in the previous 24 hours
 
	
 
• Any bleeding requiring RBC transfusion over routine transfusion needs**
 

Hemodynamic Instability			
 
• Any bleeding associated with moderate hemodynamic instability (hypotension; <math>>30</math>mmHg fall or <math>>30\%</math> decrease in either systolic or diastolic blood pressure) and requiring RBC transfusion over routine transfusion needs**
 

* Count actual bleeding (i.e. “running out” or need for basin, Kleenex, towel, etc.) not minor bleeding
 
** Red cell transfusion must be specifically related to treatment of bleeding within 24 hours of onset of bleeding
			

For inclusion, Grade 1 subset bleeding includes epistaxis, hematuria, oral petechiae, oropharyngeal bleeding, or bleeding at invasive or other wound sites. See bolded items above.
			

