### 1.9.2.2 Additional Hemostatic Therapy: All Cohorts

This product is not expected to increase the platelet corrected count increment (CCI). The infusion of platelets for six hours prior and one hour after infusion of Thrombosomes is

restricted. However, at any time, if the patient's clinical bleeding remains unchanged or deteriorates with additional or worsening bleeding, the patient's physician(s) may transfuse the patient with blood products, hemostatic agents, or coagulation factors without limitation. The study patient will be followed for safety data for 30 (+2) days post-infusion of the dose of Thrombosomes.

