### ***1.9.3 Assessment of Bleeding: Using WHO Bleeding Score***

Use of the WHO (World Health Organization) Bleeding Assessment will provide a standardized approach, across multiple clinical sites, in order to determine study eligibility, for assessing a patient's bleeding during the clinical trial, and for assessing the effect of Thrombosomes (if any) on bleeding. Study personnel conducting the assessment will be trained on the assessment and will be authorized by the PI to perform the assessment. This authorization will be documented on the Authorities and Responsibilities Log. The location of bleeding for all bleeding sites will be assessed by WHO grade during study at screening, (re-screening, if applicable) baseline, 1 hour, 6 hours, 24 hours post-infusion and 6 days post-infusion. In some instances, a bleeding site may not be able to be reassessed post-infusion due to the need for an invasive procedure or other procedure that would add additional risk for the subject. The protocol does not require subjects to undergo medically unnecessary procedures (or risks) only in order to perform post-infusion WHO bleeding assessments. Subjects who are transfused with red cells to treat anemia due to their underlying disease (and not because of bleeding) will not be assessed as having WHO grade 3 bleeding. Anemia from underlying disease will be designated if there is evidence of bone marrow suppression indicated by at least two of the following: leukopenia, thrombocytopenia, or reticulocytopenia; and absence of WHO grade 2 bleeding in the prior 24 hours. For designation of WHO grade 3 bleeding, red cell transfusion must be specifically related to treatment of bleeding within 24 hours of onset of bleeding. (see Table 4. Schedule of Events for timing of WHO bleeding assessments). The same person must perform assessment of pre-infusion and 1-hour post-infusion time points.

To assess bleeding and determine the WHO Bleeding Score, the patient will be interviewed, a physical examination will be performed, and the patient's chart will be reviewed. The WHO Bleeding Score will be determined using Appendix A- Modified WHO Bleeding Score.

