### 8.2 WHO Bleeding Severity Scores

Within multiple tables, the numbers and percentages of patients will be presented by highest WHO bleeding severity score (no bleeding/grade 0, grade 1, grade 2, grade 3, or grade 4), with "highest severity score" defined as the score associated with the most severe bleeding site (given documentation of multiple sites) for the nominal time-point of interest. This distribution of highest WHO bleeding severity scores not only will be presented by nominal time-point but also will be presented by post-baseline time-points relative to baseline time-point (to allow for assessment of shift) and by both bleeding site and time-point. Differences between patient cohorts (dose levels) in the proportion of the study population showing grade 2 or higher bleeding severity for the most severe bleeding site will be tested for statistical significance per time-point using Fisher's exact test, with results displayed in a single table. To facilitate visual examination of trends, 1 or more of the summaries described above may be presented within supplementary clustered bar charts or line chart overlays.

The numbers and percentages of patients will also be presented by grade-level change in WHO bleeding severity (-2, -1, 0, +1, +2, and +3) from baseline to post-baseline time-points for the patient's most severe bleeding site at baseline, by indication of increased bleeding severity from baseline to post-baseline time-points for the patient's most severe bleeding site at baseline, and by

indication of development of new bleeding sites from baseline to post-baseline time-points. Lastly, the details of all WHO bleeding assessments will be presented in a patient-level data listing. To facilitate, within this listing, visual examination of possible post-infusion changes in bleeding severity or number of bleeding sites as associated with protocol-defined windows for the timing of infusion relative to screening (i.e., within 24 hours [as stipulated in CSP v1.1] vs. within 4 days [as stipulated in CSP v2.0+]), the data listing will be sorted first by the screening assessment dates of patients and then, within individual patients, by assessment date.

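### For epistaxis, oropharyngeal bleeding and invasive-site oozing, the 24-hour look-back makes the 1 h and 6 h WHO grades mostly a record of pre-infusion bleeding, so early improvement is largely masked.

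*Protocol*

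**What the plan says.** Protocol Appendix A separates Grade 1 from Grade 2 for epistaxis and for oropharyngeal bleeding at 30 minutes, measured as "total duration of all episodes in previous 24 hours". Invasive-site bleeding is split at one hour, measured as "active oozing at site for a cumulative total of" up to or above that limit, again over the preceding 24 hours.

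Protocol 1.9.3 schedules the assessment at screening and then at "baseline, 1 hour, 6 hours, 24 hours post-infusion and 6 days post-infusion", and states: "The WHO Bleeding Score will be determined using Appendix A- Modified WHO Bleeding Score". No separate rule is given for the early visits. Table 4 allows the 1 h visit ±15 min, the 6 h visit -1/+2 h and the 24 h visit ±3 h. The baseline assessment is made within the 2 h before infusion.

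The effect of dose on the WHO score is a secondary objective in Protocol 1.8.2. SAP 2.2.1 places grade distribution, shift, grade-level change and increase among the primary (safety) endpoints. SAP 8.2 tabulates these at every post-baseline time-point. It also compares cohorts on the proportion at Grade 2 or above with Fisher's exact test, which "will be tested for statistical significance per time-point". When two sites tie as worst at baseline, SAP 8.2 picks the site to follow by comparing their 1 h grades, then their 6 h grades, and so on.

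**The concern.** A grade that sums bleeding over the last 24 hours cannot react quickly to a treatment given one or six hours ago. At the three duration-graded sites, a patient whose bleeding stops completely at infusion will usually keep the baseline grade at both early visits. A patient whose bleeding stopped long before infusion may drop a grade simply because the episode has left the window.

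Three things are at stake.

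- **Grade-change tables.** At these sites, the 1 h and 6 h columns are pulled toward no change, with some spurious improvement mixed in.
- **Fisher test.** At the early visits it would, for these sites, largely compare the pre-infusion histories of sequentially enrolled, non-randomised cohorts. It would be read as a dose comparison.
- **Tie-break.** A carried-over grade helps decide which site is followed. If epistaxis and gross hematuria tie at Grade 2 and the hematuria clears by 1 h, the epistaxis is selected whether or not it has stopped.

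The 1 h visit is also the one least exposed to other treatment. Protocol 1.9.2.2 says "The infusion of platelets for six hours prior and one hour after infusion of Thrombosomes is" restricted, although it lets the physician transfuse at any time if bleeding persists or worsens.

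**Working it through.** The documents give no effect size or power figure for the WHO score, so there is none to reproduce. The check is window arithmetic.

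**Inputs.** Look-back 24 h; cut-offs 30 min (nose, mouth) and 60 min (invasive sites), from Appendix A. Visit windows from Table 4: 0.75-1.25 h, 5-8 h, 21-27 h. Baseline 0-2 h before infusion.

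**1. Share of the look-back that precedes infusion** = (24 - t)/24, and zero from t = 24 h on.

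| Visit | Nominal | Range over window |
|---|---|---|
| 1 h | 23/24 = 95.8% | 94.8% (1.25 h) to 96.9% (0.75 h) |
| 6 h | 18/24 = 75.0% | 66.7% (8 h) to 79.2% (5 h) |
| 24 h | 0% | 0% to 12.5% (3/24, at 21 h) |
| Day 6 | 0% | 0% |

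**2. Overlap with the baseline look-back** = 24 - t hours if baseline is taken at infusion, 22 - t hours if taken 2 h earlier. At 1 h this is 21-23 of the 24 hours; at 6 h it is 16-18.

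**3. What full cessation would look like.** Suppose bleeding stops completely at infusion and earlier bleeding was spread evenly over 24 h (an assumption). A Grade 2 site drops to Grade 1 only if its baseline total is at most cut-off × 24/(24 - t):

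- Nose or mouth: 30 × 24/23 = 31.3 min at 1 h; 30 × 24/18 = 40 min at 6 h.
- Invasive site: 60 × 24/23 = 62.6 min at 1 h; 60 × 24/18 = 80 min at 6 h.

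If there was instead one short episode, timed at random in the 24 h before infusion, the chance that it has left the window is t/24: 4.2% at 1 h and 25% at 6 h.

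**4. Two worked patients,** with no other bleeding and no recurrence.

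- 45 min of epistaxis 10 h before infusion is 11 h old at the 1 h visit and 16 h old at the 6 h visit. It is Grade 2 at baseline, 1 h and 6 h, so the tables show no change.
- 45 min of epistaxis 20 h before infusion is 21 h old at 1 h (Grade 2) and 26 h old at 6 h (Grade 0). The tables show a two-grade improvement due only to elapsed time.

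Both are compatible with Protocol 1.9.2.1, which counts bleeding within 4 days of infusion as active.

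**5. Scope.** Appendix A has 10 Grade 1 and 16 Grade 2 entries. Three of each carry the 24-hour duration window: 6 of 26. Of the five named Grade 1 types that qualify for entry, three carry it.

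**The case against.** The strongest reply is that this is not a property of the whole score. Entries such as "Petechiae of oral mucosa" and "Any biochemical or microscopic Hb/RBCs without red urine" state no time window, nor do the skin, gastrointestinal, pulmonary, body-cavity and CNS entries. That stands. The percentages above apply only to the three duration-graded types. For the rest the look-back is unstated, which is a gap, but carry-over is not established.

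A reader might go further and infer that the 1 h and 6 h grades cannot show any effect. The documents do not support that. New sites can appear, grades can rise, and some improvement is possible at 6 h. A higher duration total can arise only from bleeding after the baseline assessment, so a recorded rise is never the clock alone. It may still overstate the change. With 28 min in the 18 h before infusion and 4 min in the 6 h after, the total is 32 min and Grade 1 becomes Grade 2, although the rate fell from 28/18 = 1.6 to 4/6 = 0.7 min/h. That calls for a footnote, not for dropping the data.

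Nor do the documents name the 1 h visit as the key comparison. They require the same assessor at baseline and 1 h, but SAP 8.2 treats all time-points alike.

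Removing the early grades from the tables for all sites would be the wrong response. SAP 2.1.1 and 2.2.1 use worsening of bleeding as a primary safety indicator, and early escalation must stay visible.

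Finally, this is a Phase 1 study with 8 patients per cohort and no statistical basis for its size. The stopping and suspension rules do not refer to the WHO grade, and no WHO table is among the DMC outputs listed in SAP Appendix 1. That limits the consequences, but it does not make the early improvement figures or Fisher results interpretable.

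**Conclusion.** The concern holds for epistaxis, oropharyngeal bleeding and invasive-site oozing. At these sites the look-back is 95-97% pre-infusion at 1 h, 67-79% at 6 h, and up to 12.5% at a 24 h visit held at 21 h. Improvement is largely masked at the two early visits, and some of what does appear reflects only elapsed time. If SAP 8.2 is followed as written, its early change columns and early Fisher tests would mislead for these sites.

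The bleeding objective as a whole is not lost: Day 6, and a 24 h visit held at 24 h or later, are free of carry-over. By then, however, the platelet restriction has been lifted for about 23 h, so a clean grade is not the same as an unconfounded one.

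The percentages rest on the stated windows alone. The limits for a Grade 2 to Grade 1 drop also assume evenly spread earlier bleeding. The number of patients affected depends on the site mix, which the documents do not give.

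**What to change.** 1. At the 1 h and 6 h visits, for these three bleeding types only, also record whether any bleeding has occurred since infusion and for how many minutes. Tabulate this as the early readout. It is descriptive, since no pre-infusion interval of matching length is recorded. Simply shortening the look-back would not work, because the 30-min and 1-h cut-offs are defined per 24 h.
2. In SAP 8.2, base grade improvement at the baseline site and the between-cohort Fisher test on the 24 h and Day 6 visits. Hold the 24 h WHO assessment at 24 h or later, for example 0/+3 h instead of ±3 h.
3. Keep the 1 h and 6 h grades in the by-visit, shift, increase and new-site tables as safety data. Add a footnote that duration-graded sites carry pre-infusion bleeding.
4. Do not use the 1 h or 6 h grades of duration-graded sites to break baseline ties. For these sites the SAP's own sequence would then go to the 24 h grade.

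Cost: one extra CRF field per affected site at two existing visits, a slightly narrower 24 h window for one assessment, and SAP wording. The sponsor also gives up any early improvement claim on the WHO grade at these sites.
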